#### 6.1.6. Analysis Visit Windows

Data in summary tables will be summarized by the nominal visit collected in the electronic data capture (EDC) system. The Day 182 (EOS or early termination [ET]) label in the EDC system is used for both Day 182 EOS visits and ET visits. A participant will only have their Day 182 data included in the summary tables if it occurs after study Day 170. Participants that early terminate before study Day 170 will have their ET visit listed only.

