4.3 Clinical Experience

CT1812 has been administered safely with good tolerability in over 60 healthy volunteers in a placebo-controlled Phase 1a trial (COG 0101). Six single (10-1120 mg) and three multiple dose cohorts (QD, 14 days, 280-840 mg) were observed under close inpatient stay (N=6-8 treated, 2 placebo per cohort). Plasma concentrations of drug were shown to be approximately dose proportional across two orders of magnitude [0.13-14.93 mg (free base equivalent)/kg], and accumulation was minimal. Peak concentrations of CT1812 were reached within 1 to 2 hours and the plasma half-life was shown to be approximately 12 hours. Adverse events were mostly mild to moderate in severity and principally included headache, nausea, vomiting, diarrhea, constipation, abdominal pain, dyspepsia, upper respiratory tract infection, lightheadedness, syncope, myalgia, dizziness, rash, and pain at the lumbar puncture site in those participants who

had lumbar punctures. There was only one AE of severe intensity, being an SAE of upper respiratory tract infection, occurring in one participant in the 840 mg dose of the MAD study, believed to be unrelated to study drug based on a similar pattern of URTIs in subjects receiving drugs other than CT1812 in the study unit during the same time period. One participant in the multiple dose cohort study developed a rash while on study drug. This participant showed improvement after discontinuing CT1812.

No evidence of renal toxicity or hypercalcemia has been observed based on routine measures of renal function (serum creatinine, BUN) or cystatin C.

Four participants in the MAD study showed an increase in liver function tests below 3X the upper limit of normal (including one participant on placebo). Subsequent studies will closely monitor liver enzyme parameters to determine if these were sporadic findings or possibly drug-related.

A fed cohort (280 mg) single dose was compared to the fasting cohort of 280 mg and no significant food effect was observed. A multiple dose cohort of elderly (≥65 years old) healthy volunteers was dosed at 560 mg x 14 days, and their exposures were similar to the 840 mg younger healthy volunteer participants.

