10.2.13 Participant Study Day 172, Serum Collection

Collect serum sample on Day 172 (+/- 2 days) (see Section 11.2 for details and the laboratory manual).

10.2.14 Participant Visit 14 / Study Day 182, End of Study Treatment Early Termination

This visit should be used as the Early Termination visit should the participant discontinue the study earlier than the Study Day 210 visit.

The participant will return to the clinic.

- Perform cognitive testing (see Section 12.1 for details).
- Perform MMSE.

- Perform complete physical examination (see Section 13.1.2 for details).
- Measure and record vital signs (see Section 13.1.3 for details).
- Draw blood and prepare sample for serum chemistry and hematology (see Section 13.1.4 for details).
- Draw blood and prepare sample for serum cystatin C (see Section 13.1.5.1 for details).
- Collect blood samples for PK and exploratory biomarker analysis (see Section 11.2 for timing of sample collection).
- Collect urine samples for urinalysis (see Section 13.1.4 for details).
- Optional: Perform lumbar puncture pre-dose (note: lumbar puncture may be performed pre-dose on Day 178, 179, 180 or 181 for ease of scheduling) (see Section 11.5 for details).
- Administer C-SSRS Since Last Visit version (see Section 13.1.6).
- Record any AEs.
- Record changes in medications.
- Conduct drug accountability on returned bottle.
- Administer Day 182 dose with or without food.

- Perform 12-lead ECG ~ 2 hours post-dose (see Section 13.1.7 for details).
- Perform MRI.

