#### 4.1. Introduction

Data processing, tabulation of descriptive statistics, calculation of inferential statistics, and graphical representations will be performed primarily using SAS (release 9.4 or higher). If the use of other software is warranted, the final statistical methodology report will detail what software was used for what purposes.

Continuous (quantitative) variable summaries will include the number of participants (n) with non-missing values, mean, standard deviation (SD), median, minimum, and maximum. Other statistics such as coefficient of variation (%CV), quartiles, confidence intervals (CIs), and number of missing values may be added as appropriate.

Categorical (qualitative) variable summaries will include the frequency and percentage of participants who are in the particular category or each possible value. In general, the denominator for the percentage calculation will be based upon the total number of participants in the study population within each treatment group, unless otherwise specified. The denominator for by-visit displays will be the number of participants in the relevant study population with non-missing data at each visit.

The minimum and maximum will be reported with the same degree of precision (i.e., the same number of decimal places) as the observed data. Measures of location (mean and median) will be reported to 1 degree of precision more than the observed data. Measures of spread (SD) will be reported to 2 degrees of precision more than the observed data.

Percentages will be presented to 1 decimal place, unless otherwise specified.

Unless otherwise indicated, all statistical tests will be conducted at the 0.05 significance level using 2-tailed tests, and P-values will be reported. A P-value of  $\leq$ 0.10 but >0.05 will be considered evidence of a trend. Corresponding 95% CIs will be presented for statistical tests.

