#### 5. Analysis Populations

The following analysis populations are planned for this study:

- All Subjects: The All Subjects population includes all participants who sign the ICF and get screened for the study.
- Safety Population (SAF): The Safety Population includes all participants who receive one or more doses of study medication.
- Efficacy Modified Intent-To-Treat Population (mITT): The Efficacy mITT Population includes all randomized participants who receive any amount of study drug and who have a baseline and at least one post-baseline assessment of the ADAS-Cog 11 total score.
- Completers Population (CP): The Completers Population includes all randomized participants who completed the study (i.e., who did not prematurely withdraw). There is no expectation that a participant included in the CP will have attended every single scheduled visit; as long as the participant completed the study, they will be included in the population.
- **Pharmacokinetic Population (PK):** The Pharmacokinetic Population includes all participants in the SAF who had at least one quantifiable concentration of CT1812.

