#### 9.2. Clinical Laboratory Evaluations

#### 9.2.1. Protocol-Required Safety Laboratory Tests

Hematology testing will include erythrocyte (red blood cell count), erythrocyte mean corpuscular hemoglobin concentration (MCHC), erythrocyte mean corpuscular volume (MCV), hematocrit, hemoglobin, and absolute counts of leukocytes, lymphocytes, monocytes, neutrophils, basophils, eosinophils, and platelets. Coagulation testing (prothrombin time [PT/INR]) will be performed at screening and Day 154 only.

Serum chemistry analyses will include glucose, calcium, albumin, protein, sodium, potassium, bicarbonate, chloride, magnesium, fractional calcium excretion, blood urea nitrogen (BUN), creatinine, creatine kinase, alkaline phosphatase, Alanine Aminotransferase (ALT), Aspartate Aminotransferase (AST), bilirubin, lipase, lactate dehydrogenase (LDH), and phosphate.

Urinalysis will include osmolality, creatinine, calcium, erythrocytes, leukocytes, sodium, specific

gravity, pH, specimen appearance (turbidity), color, protein, glucose, ketones, bilirubin, hemoglobin, urobilinogen, nitrite, and microscopic particles. Trace protein will be considered positive. Urine samples that did not have preservative added prior to lab analysis will be listed only.

All summaries of laboratory values from local and central lab will be presented using SI units. Observed hematology, chemistry, and urinalysis values and changes from baseline at each visit will be summarized by treatment received. Shifts from baseline regarding low/normal/high values will also be summarized by treatment received.

Shift tables summarizing the most extreme post-baseline shift for each participant within each lab parameter will be presented, with low and high results considered more extreme than normal. If a participant has both a low and high post-baseline result within a parameter, they will be counted within both the low and high rows.

The incidence of post-baseline ALT values  $\ge 3xULN$ , AST values  $\ge 3xULN$ , and AST or ALT values  $\ge 3xULN$  will be summarized.

All chemistry, hematology, and urinalysis data will be listed.

Screening laboratory tests such as viral serology, thyroid stimulating hormone, follicle-stimulating hormone, HbA1c, Folate, B12, and urine pregnancy test results will be listed only.

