#### 9.6. Columbia Suicide Severity Rating Scale (C-SSRS)

The C-SSRS is routinely used to quantify the severity of suicidal ideation and behavior. Both the ideation and behavior subscales are sensitive to change over time.

Two versions of the C-SSRS will be used in this study: the Screening version and the Since Last Visit version. The Screening version of the C-SSRS assesses lifetime suicidal ideation and behavior. The Since Last Visit version of the C-SSRS assesses suicidal thoughts or behaviors the participant may have had since the last time the C-SSRS was administered.

At the screening visit, the C-SSRS Screening version will be administered. At all subsequent visits, the C-SSRS Since Last Visit version will be administered.

The C-SSRS includes "yes" or "no" responses for assessment of suicidal ideation and behavior as well as numeric ratings for severity of ideation, if present (from 1 to 5, with 5 being the most severe). Assign a score of 0 if no ideation is present.

Suicidal Ideation items include:

Category 1 – Wish to be Dead

Category 2 – Non-specific Active Suicidal Thoughts

Category 3 – Active Suicidal Ideation with Any Methods (Not Plan) without Intent to Act

Category 4 – Active Suicidal Ideation with Some Intent to Act, without Specific Plan

Category 5 – Active Suicidal Ideation with Specific Plan and Intent

Suicidal Behavior items include:

Category 6 – Preparatory Acts or Behavior

Category 7 – Aborted Attempt

Category 8 – Interrupted Attempt

Category 9 – Actual Attempt (non-fatal)

Category 10 – Completed Suicide

Self-injurious behavior without suicidal intent is also a C-SSRS outcome (although not suicide-related) and has a binary response (yes/no).

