#### **Endpoints:**

Composite endpoints based on the above categories are defined below:

- Suicidal **ideation**: A "yes" answer at any time during treatment to any one of the five suicidal ideation questions (Categories 1-5) on the C-SSRS.
- Suicidal **behavior**: A "yes" answer at any time during treatment to any one of the five suicidal behavior questions (Categories 6-10) on the C-SSRS.

• Suicidal **ideation or behavior**: A "yes" answer at any time during treatment to any one of the ten suicidal ideation and behavior questions (Categories 1-10) on the C-SSRS.

Baseline is defined as the most severe ideation and behavior reported in the past 6 months prior to the first dose of study drug. Suicidality data collected on the C-SSRS will be listed for all participants with at least one occurrence of suicidal ideation or behavior during treatment. Tables will include results from the Suicidal Ideation and Suicidal Behavior sections of the C-SSRS. Frequencies and percentages of participants with a response of "Yes" at any point as well as by study visit on the Suicidal Ideation and Suicidal Behavior items will be summarized by treatment received.

Additionally, shifts of whether participants experienced suicidal ideation, behavior, or both from pre-treatment to post-treatment will be summarized in a shift table. An additional shift table of maximum ideation from pre-treatment to post-treatment will also be provided.

All C-SSRS data will be listed.

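### SAP 6.1.6 does not confine its listed-only rule for early-termination visits to by-visit tables; read literally, it drops withdrawal-visit labs and C-SSRS from three any-time safety summaries

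*SAP*

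**What the plan says.** **The rule.** SAP 6.1.6 (Analysis Visit Windows) begins with tables organised by nominal visit. It then explains that one label in the data capture system, Day 182, serves both the scheduled end-of-study visit and the early-termination (ET) visit. Data under that label enter the summary tables only when collected after Day 170, and "Participants that early terminate before study Day 170 will have their ET visit listed only".

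**The visit it applies to.** Protocol 10.2.14 lists the Day 182 procedures, which include chemistry, hematology, C-SSRS and cognitive testing, and says "This visit should be used as the Early Termination visit should the participant discontinue the study earlier than the Study Day 210 visit". Protocol 9.5.1 places the ET visit within 2 weeks of the last dose.

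**The summaries that are not by visit.** SAP 9.2.1 says "Shift tables summarizing the most extreme post-baseline shift for each participant within each lab parameter will be presented", and also plans the incidence of post-baseline ALT and AST values at or above 3 x ULN. SAP 9.6 counts C-SSRS yes responses "at any point as well as by study visit". Neither section mentions ET visits. The Since Last Visit form, used after screening, "assesses suicidal thoughts or behaviors the participant may have had since the last time the C-SSRS was administered".

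**Denominators.** SAP 4.1 sets the general rule that "the denominator for the percentage calculation will be based upon the total number of participants in the study population within each treatment group". By-visit displays instead use participants with data at that visit.

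**Efficacy.** The repeated-measures model (SAP 8.1) uses Days 42, 98 and 182. SAP 8 treats a Day 182 visit outside Days 171 to 193 as out of window. The one population-based sensitivity analysis uses the Completers Population, which SAP 5 restricts to participants who did not withdraw early.

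**The concern.** Safety is the primary objective, and the ET visit is the last full safety assessment of someone who leaves. A programmer who applies 6.1.6 as written would exclude that visit from every table, including the three that are meant to pick up a result whenever it occurs. A liver-enzyme value or a suicidality response seen first, or at its worst, at the ET visit would then appear only in a listing, while by default the participant still counts in the denominator.

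The C-SSRS is the most exposed. Each form covers only the time since the previous one, so if the ET form is left out, no other form covers the days between the last scheduled visit and withdrawal.

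There is a smaller question on efficacy. The protocol asks for scores at the ET visit, but no rule assigns those obtained before Day 170 to a modelled visit, and the Completers analysis removes these participants altogether. SAP 6.1.4 does not say whether ET scores would be carried forward if the LOCF fallback were used.

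**Working it through.** **1. The plan's own safety figure.** SAP 3.2 gives 91% for seeing at least one case of a drug-related AE with 5% prevalence among 48 participants. Check: 1 - 0.95^48 = 0.915. It reproduces. It refers to AEs, and SAP 9.1 defines a treatment-emergent AE by onset on or after first dose, with no visit restriction. The ET rule does not touch it.

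**2. How many ET visits.** Inputs: 144 participants and 15% dropout (SAP 3.2; Protocol synopsis). 0.15 x 144 = 21.6, or 7.2 per arm. This is an upper bound: it assumes that every dropout attends an ET visit before Day 170. If withdrawals are spread evenly over 182 days (assumed):
- ET visit on the day of withdrawal: 21.6 x 170/182 = 20.2.
- ET visit 14 days later: 21.6 x 156/182 = 18.5.

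For dropout of 5% to 30% (assumed range) the upper bound is 7.2 to 43.2.

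**3. Time covered only by the ET C-SSRS.** Nominal C-SSRS days before Day 170 (SAP Table 1) are 1, 7, 14, 28, 42, 56, 70, 98, 126 and 154, plus 3 and 21 in Parts A and B. For each withdrawal day from 1 to 169, count the days since the last scheduled form and average:
- Part C: 1654/169 = 9.8 days.
- Parts A and B: 1597/169 = 9.4 days.
- Maximum: 27 days, because visits after Day 70 are 28 days apart. The visit windows of plus or minus 2 days can shift this slightly.

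**4. Share of on-treatment look-back, if events are unrelated to withdrawal.** With 15% dropout, even timing and the Part C schedule:
- ET-only days per participant: 0.15 x 9.79 x 169/182 = 1.36.
- On-treatment days per participant: 0.85 x 182 + 0.15 x 91 = 168.35.
- Share: 1.36/168.35 = 0.8%.

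The same formula gives 0.45/177.45 = 0.3% at 5% dropout and 2.73/154.7 = 1.8% at 30%.

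**5. Weight of one uncounted participant.** 1/96 = 1.0 percentage point in the pooled CT1812 group; 1/48 = 2.1 points in one dose arm.

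**6. Efficacy, by comparing the text.** A score from an ET visit before Day 170 is not a Day 42 or Day 98 nominal visit and falls outside Days 171 to 193, so by inference it enters no repeated-measures model. It may also be an off-drug value. Protocol 4.3 reports that "the plasma half-life was shown to be approximately 12 hours", and 14 days is 14 x 24/12 = 28 half-lives.

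**The case against.** The best defence is that the rule was never meant to reach the any-time summaries. The section concerns visit windows and opens with by-visit tables. Its evident purpose is to stop an early withdrawal visit from being tabulated as Day 182 merely because the two share a label. SAP 9.2.1 and 9.6 use their own terms, and 9.6 itself separates any-time from by-visit counts. This stands as the more natural reading, but the SAP does not state it and the literal words go further.

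The safety net is also wider than these three summaries. Clinically significant laboratory abnormalities are AEs (Protocol 13.2.1), and AEs leading to discontinuation have their own table (SAP 9.1.1). An enzyme rise that stops dosing would normally be measured before the ET visit. Earlier scheduled results still count, and all laboratory and C-SSRS data are listed. All of this stands and limits the harm. It does not settle which records the three summaries should use.

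A reader might infer three stronger points, which the documents do not support:
- **That the 91% detection figure falls.** It concerns AEs, whose tables are untouched. Any lower figure for laboratory or C-SSRS events needs an assumed share recorded only at the ET visit, and the documents give none.
- **That Day 170 is left unassigned.** Inclusion requires a visit after Day 170, so Day 170 is excluded, in agreement with Section 8.
- **That leaving ET scores out of the efficacy model is an error.** Keeping off-schedule and possibly off-drug values out of the main estimate is defensible, and all efficacy analyses are exploratory.

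**Conclusion.** The point holds as an ambiguity with a literal reading that would do harm. It is not proof that data will be dropped. As written, 6.1.6 can remove ET laboratory and C-SSRS results from three any-time safety summaries while the participants stay in the default denominators.

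The likely loss is small: about 0.8% of C-SSRS look-back if events are unrelated to withdrawal, given 15% dropout and even withdrawal timing. That figure is for the C-SSRS only; there is no equivalent for laboratory values. The loss grows only if events cluster at withdrawal, which the documents neither quantify nor exclude. The case for acting is that safety is the primary objective and one sentence removes the doubt.

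The efficacy gap exists, but it calls for no more than an optional sensitivity analysis. Any bias in the Day 182 contrast would need worsening after the last modelled visit, or dropout, to differ by arm, and the documents give no basis for sizing it.

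**What to change.** **Needed, in SAP 6.1.6:**
1. State that the listed-only rule applies to by-visit summaries. State that all post-baseline results, ET visits included, count in the most-extreme laboratory shift, the ALT/AST 3 x ULN incidence and the any-point C-SSRS summary.
2. Give Day 182 the same window as Section 8 (Days 171 to 193), since 6.1.6 sets no upper limit. Day 170 is already excluded.

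**Optional, exploratory only.** Keep the ET-excluded model as primary. Before unblinding, prespecify one sensitivity repeated-measures model for ADAS-Cog 11, and if wanted ADCS-ADL, MMSE and ADCS-CGIC. It would map ET scores to Day 42, 98 or 182 by bounded study-day windows, only where that visit has no scheduled assessment. Report days since last dose by arm, and say whether ET scores would feed the LOCF fallback. State the downside too: scores taken up to 2 weeks after the last dose can dilute a real effect, so this model does not always reduce bias.

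**Cost.** The needed part is a few sentences and a check of the table programs. The optional part adds visit-mapping code and one model per scale. Neither needs new data.

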#### **6.1.7.** Pooling of Sites

Not applicable.

#### 6.1.8. Derived Variables

- Change from baseline = value at current time point value at baseline.
- Treatment-emergent AE (TEAE) = any AE with an onset date/time on or after the first dose of study drug.
- Modified Hachinski total score = the sum of the individual 8 item scores. Items 1, 6, 7 & 8 attract a score of 2-points if present (range of 0-8). Items 2, 3, 4 & 5 attract a score of 1-point if present (range of 0-4). The total score ranges from 0 12.
  - The sites were originally responsible for manually calculating the total score and entering it into the clinical study database. To ensure accuracy, it was decided to re-derive this total score in the ADaM dataset.
- ADCS-ADL total score = the sum of the individual 23 item scores. The score ranges from 0-78.
  - The sites were originally responsible for manually calculating the total score and entering it into the clinical study database. To ensure accuracy, it was decided to re-derive this total score in the ADaM dataset
- The ADAS-13 total score = the sum of all 13 individual items (word recall; commands; constructional praxis; delayed word recall; naming objects and fingers; ideational praxis; orientation; word recognition; remembering test instructions; spoken language; word finding; comprehension of spoken language; and number cancellation).
  - The score for the number cancellation item was originally set up to be derived within the clinical study database, however prior to database lock, an error was discovered in the derivation of this item score. This error subsequently impacts

the derivation of the ADAS-13 total score, which was also originally set up to be derived within the clinical study database.

- As a result, both the number cancellation item score and the ADAS-13 total score will be re-derived in the ADaM dataset for analysis purposes as follows:
- The number cancellation score will be derived in two steps:
  - Step 1: Calculate the preliminary number cancellation item score as (number of targets hit) – [(number of errors) + (number of times to remind to task)]
  - Step 2: Take the preliminary number cancellation item score calculated in Step 1 and re-scale as follows:
    - If number cancellation item score is > 30 then re-scale as 0
    - If  $24 \le$  number cancellation item score  $\le 29$  then re-scale as 1
    - If  $18 \le$  number cancellation item score  $\le 23$  then re-scale as 2
    - If 12 < number cancellation item score < 17 then re-scale as 3
    - If  $6 \le$  number cancellation item score  $\le 11$  then re-scale as 4
    - If  $0 \le \text{number cancellation item score} \le 5 \text{ then re-scale as } 5$ 
      - Number cancellation item scores < 0 will be re-scaled as 5
  - The resulting final number cancellation item score will range from 0 to 5.
- The ADAS-13 total score will be derived as the sum of the 13 individual items, but using the score for the number cancellation item which has been re-derived as described above.
- The ADAS-11 total score is the sum of 11 individual items excluding delayed recall and number cancellation.
- The Cognitive Composite score will be calculated using z-scores of the below items. The z-scores will be derived by calculating the baseline mean and standard deviation of each individual component for all participants. A z-score within each component will be derived for each participant at each timepoint by subtracting the corresponding baseline mean and then dividing by the corresponding baseline SD. The Cognitive Composite score will be set as the mean of the 10 individual z-scores (5 ADAS-COG scores and 5 NTB scores) within each participant and timepoint. If a participant is missing one, two, or three scores at a particular timepoint, the missing scores will be set as the average non-missing z-score of all participants at that timepoint within each component when deriving the Cognitive Composite score. If a participant is missing four or more individual components at each timepoint, the Cognitive Composite score will not be derived.
  - o ADAS-COG
    - Word recall (scored on a 0 to 10 range), average of trials I, II, and III. If at least one of the trials is missing, this component will be considered missing. The sign of the z-score for this component will be reversed when deriving the Cognitive Composite score as it is the total words not recalled that is being recorded. This test is a key measure of episodic memory.

- Orientation (0 to 8). The sign of the z-score for this component will be reversed when deriving the Cognitive Composite score as the recorded score for this test is the number of items answered incorrectly. This measure is an index of the study participant's episodic memory and a single item of semantic memory (their name).
- Delayed Word Recall (0 to 10). The sign of the z-score for this component will be reversed when deriving the Cognitive Composite score as it is the total words not recalled that is being recorded.
- Word Recognition (0 to 24). The sign of the z-score for this component will be reversed when deriving the Cognitive Composite score. This is a further test of episodic memory using a word recognition paradigm of 12 true positive targets and 12 foil items. While the possible score for this measure is 0 to 24, the standard ADAS-Cog score is capped at a maximum worst score of 12.
- Number Cancellation (raw score 0 to 40, subsequently re-scaled to a 5-point scale [0-5]). In this task, the participant is asked to cross off as many target digits as possible in 45 seconds. The score is derived as the number of incorrectly crossed-off items and the number of reminders given subtracted from the number of items correctly crossed off. The resulting score (0-40) is then re-scaled to a 5-point scale (0-5) as described earlier in this section. NTB
  - COWAT This test of working memory and executive function yields a key metric referred to as 'Total number of acceptable words'. This is obtained by calculating how many of the study participant's responses are deemed acceptable according to the scoring rules. The total score for COWAT is the sum of the number of accepted words for each of the 3 tests (three letters). The score range for this test is typically between 0 and 80, though floor performance (a score of 0) is vanishingly rare in mild-to-moderate stage AD participants.
  - CFT This is a further test of working memory and executive function that yields a key metric referred to as 'Total number of acceptable words'. This is obtained by calculating how many of the study participant's responses are deemed acceptable according to the scoring rules. The usual performance range for this test is between 0 and 40.
  - Digit Span This is a brief measure of working memory, especially in the Digits Backwards section. The key metric is 'Total number of trials correct', which is the number of sequences correctly recalled. The range of the test is 0 to 24 and both floor and ceiling effects are rare.
  - Trail Making Test (TMT) A This is essentially a measure of attention, as successful completion relies on quickly and accurately connecting numbered circles in an ascending sequence. The key metric for analysis

purposes is 'Time taken for completion'. Errors and time taken once again both contribute to performance. However, because errors incur a time penalty, it is not necessary to analyze both metrics. The sign of the z-score for this component will be reversed when deriving the Cognitive Composite score.

- Trail Making Test (TMT) B This is the more complex component of the TMT in which successful completion relies on the study participant accurately connecting the numbered and lettered circles. Study participants are required to alternate between numbers and letters in an ascending sequence. The key metric for analysis purposes is again 'Time taken for completion'. As with TMT A, because errors incur a time penalty, it is not necessary to factor in errors for analysis purposes. The sign of the z-score for this component will be reversed when deriving the Cognitive Composite score.
- The Memory composite score will be a composite z-score average similar to the Cognitive Composite score but will only be derived using the average of the ADAS-Cog Word Recall, Orientation, Delayed Word Recall, and Word Recognition items. If a participant is missing any of the four items at a timepoint, this composite score will not be derived.
- The Attention composite score will be a composite z-score average derived using the average of the Number Cancellation and TMT A items. If a participant is missing either of the two items at a timepoint, this composite score will not be derived.
- The Executive function composite score will be a composite z-score average derived using the average of the COWAT, CFT, Digit Span, and TMT B items. If a participant is missing any of the four items at a timepoint, this composite score will not be derived.

